8.3.2. Method of Detecting Adverse Events and Serious Adverse Events

Care will be taken not to introduce bias when detecting AEs and/or SAEs. Open-ended and nonleading verbal questioning of the subject is the preferred method to inquire about AE occurrences.

8.3.3. Follow-up of Adverse Events and Serious Adverse Events

After the initial AE/SAE report, the investigator is required to proactively follow each subject at subsequent visits/contacts. All SAEs and AEs of special interest (as defined in [Section 8.3.6](#)) will be followed until resolution, stabilization, the event is otherwise explained, or the subject is lost to follow-up (as defined in [Section 7.3](#)). Further information on follow-up procedures is provided in [Section 10.3.3](#).

8.3.4. Regulatory Reporting Requirements for Serious Adverse Events

- Prompt notification by the investigator to the sponsor or designee of an SAE is essential so that legal obligations and ethical responsibilities towards the safety of subjects and the safety of a study drug under clinical investigation are met.
- The sponsor has a legal responsibility to notify both the local regulatory authority and other regulatory agencies about the safety of a study drug under clinical investigation. The sponsor will comply with country-specific regulatory requirements relating to safety reporting to the regulatory authority, IRBs/IECs, and investigators.
- An investigator who receives an investigator safety report describing an SAE or other specific safety information (eg, summary or listing of SAEs) from the sponsor or designee will review and then file it along with the Investigator's Brochure and will notify the IRB/IEC, if appropriate, according to local requirements.
- Investigator safety reports must be prepared for suspected unexpected serious adverse reactions (SUSARs) according to local regulatory requirements and sponsor or designee policy and forwarded to investigators as necessary.

8.3.5. Pregnancy

- Details of all pregnancies after the start of study drug and until 8 weeks after the last dose of study drug in female subjects and, if indicated, female partners of male subjects will be collected.
- If a pregnancy is reported, the investigator will record pregnancy information on the appropriate form and submit it to the sponsor or designee within 24 hours of learning of a pregnancy in a female subject or female partner of male subject (after obtaining the necessary signed informed consent from the female partner, as applicable).

- While pregnancy itself is not considered to be an AE or SAE, any pregnancy complication or elective termination of a pregnancy for medical reasons will be reported as an AE or SAE.
- Abnormal pregnancy outcomes (eg, spontaneous abortion, fetal death, stillbirth, congenital anomalies, ectopic pregnancy) are considered SAEs and will be reported as such (refer to [Section 10.3.4](#))
- The subject/pregnant female partner will be followed to determine the outcome of the pregnancy. The investigator will collect follow-up information on the subject/pregnant female partner and the neonate, and the information will be forwarded to the sponsor or designee.
- Any poststudy pregnancy-related SAE considered reasonably related to the study drug by the investigator will be reported to the sponsor or designee as described in [Section 8.3.4](#). While the investigator is not obligated to actively seek this information in former study subjects/pregnant female partner, he/she may learn of an SAE through spontaneous reporting.
- Any female subject who becomes pregnant while participating in the study will discontinue study drug.

8.3.6. Events of Special Interest

Based on the class effects or potential risks with IL-17 inhibitors, the following events of special interest (preferred term) will be monitored:

- Candida infection
- Inflammatory bowel disease.

In addition, based on the potential risk with an IL-17 receptor inhibitor the following events of special interest will also be monitored:

- suicidal ideation
- malignancies
- MACE (major adverse cardiovascular and cerebrovascular events : cerebrovascular accident and transient ischemic attack, non-fatal myocardial infarction or unstable angina, cardiovascular death)
- TB
- infections (serious, opportunistic, or fungal only)
- cytopenias
- systemic hypersensitivity reactions.

8.3.7. Overdose

These events are only considered AEs or SAEs if there are associated clinical signs and symptoms or if the act of taking the excess medicine itself is an AE or SAE (eg, suicide attempt). Refer to [Section 6.7](#).

If an overdose occurs associated with an SAE in the course of the study, then the investigator follows the immediate safety reporting requirement for SAE with describing the overdose in an SAE description.

8.4. Pharmacokinetics

- Blood samples will be collected for measurement of plasma concentrations of izokibep as specified in the SoA ([Section 1.3](#)).
- Instructions for the collection and handling of biological samples will be provided in the Laboratory Manual by the sponsor or designee. The actual date and time (24-hour clock time) of each sample will be recorded.
- Samples will be used to evaluate the PK of izokibep. Each plasma sample will be divided into 2 aliquots (1 each for PK, and a backup). Samples collected for analyses of izokibep (plasma) concentration may also be used to evaluate safety or efficacy aspects related to concerns arising during or after the study.
- Genetic analyses will not be performed on these plasma samples.
- Study drug concentration information will not be reported to investigative sites.
- Pharmacokinetic samples will be shipped frozen from clinical sites to the central laboratory and later shipped from central laboratory to the PK laboratory for analysis. The PK plasma samples will be stored in a secure storage space with adequate measures to protect confidentiality.
- The PK plasma samples will be retained while research on izokibep or interventions of this class or PsA continues but no longer than 20 years or other period as per local requirements.

8.5. Genetics

Not applicable.

8.6. Biomarkers

Not applicable.

8.7. Immunogenicity Assessments

- Antibodies to izokibep will be evaluated in serum samples collected from all subjects according to the SoA ([Section 1.3](#)). Additionally, serum samples should also be collected at the final visit from subjects who discontinued study drug or were withdrawn from the study. These samples will be tested by the sponsor or sponsor's designee.
- Instructions for the collection and handling of biological samples will be provided in the Laboratory Manual by the sponsor or designee.
- Samples testing positive for binding antibodies may be further characterized and may be tested for neutralizing antibodies.
- The detection and characterization of antibodies to izokibep will be performed using a validated assay method by or under the supervision of the sponsor.
- The immunogenicity serum samples will be retained while research on izokibep or interventions of this class or PsA continues but no longer than 20 years or another period as per local requirements.

8.8. Health Economics

Refer to [Section 8.1.2.8](#).

9. Statistical Considerations

This section is a summary of the planned statistical analyses of the most important endpoints including primary and secondary endpoints.

9.1. Statistical Hypotheses

The primary objective of this study is to demonstrate that izokibep (160 mg dosed QW or 160 mg dosed Q2W) is superior to placebo in the proportion of subjects achieving ACR50 at Week 16 of the study. The statistical null and alternative hypotheses to be used to assess the primary objective are:

$$H_0: \pi_{ABY} - \pi_{PBO} = 0$$

$$H_A: \pi_{ABY} - \pi_{PBO} \neq 0$$

Where π_{ABY} and π_{PBO} are the proportion of subjects achieving ACR50 at Week 16 among subjects randomly assigned to receive izokibep and placebo, respectively. One set of hypotheses will be tested for each dose frequency of izokibep 160 mg (QW and Q2W).

Analogous statistical hypotheses will be used for the secondary objective of assessing the proportion of subjects achieving PASI90 at Week 16 among subjects with $\geq 3\%$ BSA psoriasis at baseline, the proportion of subjects achieving resolution of enthesitis at Week 16 among subjects that had enthesitis at baseline, achievement of MDA at Week 16, the proportion of subjects achieving ACR20 at Week 16 compared to baseline, the proportion of subjects achieving improvement in PsAID of at least 3 units at Week 16 compared to baseline in subjects with PsAID ≥ 3 at baseline.

The statistical null and alternative hypotheses to be used to assess the secondary objective of change in physical function of HAQ-DI from baseline to Week 16 are:

$$H_0: \mu_{ABY} - \mu_{PBO} = 0$$

$$H_A: \mu_{ABY} - \mu_{PBO} \neq 0$$

Where μ_{ABY} and μ_{PBO} are the mean change from baseline to Week 16 among subjects randomly assigned to receive izokibep and placebo, respectively. One set of hypotheses will be tested for each dose frequency of izokibep 160 mg (QW and Q2W).

9.1.1. Multiplicity Adjustment and Type I Error Rate

Hypotheses tested will be adjusted to control the familywise error rate in the strong sense at $\alpha = 0.05$, 2-sided.

The statistical comparisons for the primary efficacy endpoint and the secondary endpoints, all at Week 16, will be carried out in sequential order. The primary endpoint, comparing izokibep dosed QW to placebo, will be tested first, with significance concluded if $p < 0.05$.

Testing of secondary endpoints, comparing izokibep dosed QW to placebo, will only be carried out if all prior tests, including the tests of the primary endpoint, first show significance with $p < 0.05$. If all primary and secondary endpoints, comparing izokibep doses QW to placebo, are

significant, testing of izokibep doses Q2W to placebo will begin and follow the same order. As long as all prior tests are significant, testing will proceed in the following order:

- The primary endpoint, achieving ACR50 at Week 16, comparing izokibep dosed QW to placebo.
- The first secondary endpoint, achieve PASI90 at Week 16 in subjects with $\geq 3\%$ BSA psoriasis at baseline, comparing izokibep dosed QW to placebo.
- The second secondary endpoint, achieving resolution of enthesitis at Week 16 in subjects that had enthesitis (LEI > 0) at baseline, comparing izokibep dosed QW to placebo.
- The third secondary endpoint, achieving MDA at Week 16, comparing izokibep dosed QW to placebo.
- The fourth secondary endpoint, achieving ACR20 at Week 16, comparing izokibep dosed QW to placebo.
- The fifth secondary endpoint, achieving improvement in PsAID of at least 3 units at Week 16 compared to baseline in subjects with PsAID ≥ 3 at baseline, comparing izokibep dosed QW to placebo.
- The sixth secondary endpoint, change in physical function of HAQ-DI from baseline to Week 16, comparing izokibep dosed QW to placebo.
- The primary endpoint, achieving ACR50 at Week 16, comparing izokibep dosed Q2W to placebo.
- The first secondary endpoint, achieve PASI90 at Week 16 in subjects with $\geq 3\%$ BSA psoriasis at baseline, comparing izokibep dosed Q2W to placebo.
- The second secondary endpoint, achieving resolution of enthesitis at Week 16 in subjects that had enthesitis (LEI > 0) at baseline, comparing izokibep dosed Q2W to placebo.
- The third secondary endpoint, achieving MDA at Week 16, comparing izokibep dosed Q2W to placebo.
- The fourth secondary endpoint, achieving ACR20 at Week 16, comparing izokibep dosed Q2W to placebo.
- The fifth secondary endpoint, achieving improvement in PsAID of at least 3 units at Week 16 compared to baseline in subjects with PsAID ≥ 3 at baseline, comparing izokibep dosed Q2W to placebo.
- The sixth secondary endpoint, change in physical function of HAQ-DI from baseline to Week 16, comparing izokibep dosed Q2W to placebo.

9.2. Analysis Sets

Full Analysis Set

For assessing the primary and secondary efficacy objectives, all subjects randomized will be included in the analyses as the Full Analysis Set. Intercurrent events such as missed or discontinued treatment and protocol deviations will be addressed as described in the definition of the estimands in [Section 9.3](#). Subjects will be included according to randomized treatment assignment.

Safety Analysis Set

For assessing the safety objectives, all subjects randomized who receive at least 1 administration of test material will be included in the summaries and analyses. In the event that a subject receives incorrect study drug, that subject will be grouped according to treatment received, and such subjects will be listed and counted in the final report.

PK Analysis Set

For assessing PK parameters, all subjects who receive at least 1 administration of test material and have at least 1 sample collected and analyzed for drug concentration will be included in summaries and analyses.

ADA Analysis Set

For assessing ADA, all subjects who receive at least 1 administration of test material and have both baseline ADA and at least 1 postdose ADA measurements will be included in summaries and analyses.

9.3. Statistical Analyses

9.3.1. General Considerations

All data collected will be summarized by planned timepoint without imputation. Continuous data will be summarized with count, mean, Q1, median, Q3, standard deviation, minimum, and maximum. Change from baseline will additionally include standard error. Categorical data will be summarized with count and percent. Time to event data will be summarized with product-limit estimators of median and quartiles.

All hypothesis tests will be reported with 2-sided *p*-values. Comparison of QW dosing to placebo will use only subjects assigned to receive izokibep 160 mg QW or placebo; comparison of Q2W dosing to placebo will use only subjects assigned to receive izokibep 160 mg Q2W or placebo; comparison of Q4W izokibep to placebo will use only subjects assigned to receive izokibep 80 mg Q4W or placebo. All confidence intervals will be 2-sided with nominal 95% coverage.

Data will be summarized by planned timepoint, using data collected at the visit. Study day will be calculated as postbaseline date minus randomization date, plus 1 (except that study day for pre-randomization dates will not include the plus 1). Day range windows will not be applied for summaries (but may be applied for protocol deviations). Baseline values will be the last value collected before randomization and change from baseline will be calculated as postbaseline value minus baseline value.

Stratified tests will use the strata of prior TNFi use (Yes/No) and enthesitis at baseline (LEI = 0 versus > 0) from the randomization process. If a subject is incorrectly classified into a stratum during the randomization process, the analysis will use the correct classification, not the classification used during randomization.

Primary and secondary endpoints will be tested using only three treatment groups: izokibep 160 mg Q2W, izokibep 160 mg QW and placebo. The treatment group receiving izokibep 80 mg Q4W will only be used for exploratory analyses and endpoints.

9.3.2. Primary Endpoint and Estimand

The primary endpoint is ACR50 response, as defined in [Section 3](#). The primary analysis will occur when all subjects have had the opportunity to complete at Week 16 visit or discontinued the study.

The statistical comparisons for the primary efficacy endpoint and the secondary endpoints, all at Week 16, will be carried out in sequential order. The primary endpoint, comparing izokibep dosed QW to placebo, will be tested first, with significance concluded if $p < 0.05$. Testing of secondary endpoints, comparing izokibep dosed QW to placebo, will only be carried out if all prior tests, including the tests of the primary endpoint, first show significance with $p < 0.05$. If all primary and secondary endpoints, comparing izokibep doses QW to placebo, are significant, testing of izokibep doses Q2W to placebo will begin and follow the same order.

The primary efficacy analyses will use the treatment policy estimands, using all available data from all randomized subjects regardless of treatment discontinuation, concomitant medication, protocol deviations, or other actions. Subjects will be analyzed in the group to which they are randomized. Subjects who do not have an evaluation for a dichotomous endpoint at a given timepoint will be imputed as nonresponders.

The null hypothesis of equal response rates will compare each dosing regimen of izokibep to the placebo group. A stratified test of response rates will be used. Within each of the strata used for randomization, the response rate for each treatment group and corresponding standard error will be calculated. If a subject is incorrectly classified into a stratum during the randomization process, the analysis will use the correct classification, not the classification used during randomization. The difference in response rates (risk difference) will be calculated for each stratum. The common risk difference among the strata and associated standard error will be estimated by combining the observed risk differences using Cochran-Mantel-Haenszel weighting. The estimated risk difference divided by the standard error will be used as the test statistic and a p -value calculated assuming that the test statistic follows a standard normal distribution under the null hypothesis. Analyses at earlier timepoints when data to calculate the ACR50 are collected will also be presented using the same methodology. P -values from earlier timepoints will be presented for descriptive purposes, not part of the alpha-preserving multiple testing strategy.

A tipping point analysis will be performed in order to evaluate the robustness of the results of the primary analysis. This analysis will use simulations to assess the impact of different response rates in subjects with missing primary endpoint data, and how different the response rates must be to change the conclusions of the study. The tipping point analysis will impute mean response

rates in the two groups. Imputed response rates will be based on the response rates among subjects with observed primary endpoint data at Week 16. Sets of imputed mean response rates will include the observed response rates ($\hat{\pi}_{ABY}$, $\hat{\pi}_{PBO}$), and rates that differ in increments of ± 0.02 , adjusted independently in each arm. For each set of imputed mean response rates, 1000 simulations will be reported. Within each simulation, a random number mechanism will be used to assign each subject who is missing the primary endpoint at Week 16 to either response or non-response. The primary stratified analysis will be reported on each simulation, and the probability that the null hypothesis of equal response rates is rejected will be reported for each set of imputed response rates. A graphical output will summarize the rejection probability for various sets of response rates. The same tipping point analysis will be performed with another dose regimen of izokibep group, ie, izokibep Q2W compared to the placebo group.

Other sensitivity and supplementary analyses will be used to assess the impact of missing data assumptions and other intercurrent events. These will be defined before the database is unblinded.

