4.1. Overall Design

This is a multicenter, randomized, double-blind, placebo-controlled, Phase 2b/3 study. The plan is to evaluate the efficacy and safety of izokibep in subjects with active PsA who are TNFi naïve, who have had an inadequate response or intolerance to TNFi, or for whom TNFi is contraindicated.

Approximately 325 subjects with active PsA will be enrolled. The study consists of up to a 28-day (4-week) screening period, a 51-week treatment period, and a follow-up period with visits at 8 weeks and 14 weeks after the last dose of study drug to assess safety and immunogenicity.

Subjects meeting eligibility criteria will be randomized into 1 of 4 treatment groups in a 4:4:4:1 ratio as follows:

- Group 1 (n = 100): placebo QW from Day 1/Week 0 to Week 15, then izokibep 160 mg QW from Week 16 to Week 51.
- Group 2 (n = 100): izokibep 160 mg QW from Day 1/Week 0 to Week 51.
- Group 3 (n = 100): izokibep 160 mg Q2W from Day 1/Week 0 to Week 50, with matching placebo Q2W until Week 51 for the weeks in between izokibep doses to maintain the blind.
- Group 4 (n = 25): izokibep 80 mg Q4W from Day 1/Week 0 to Week 48, with matching placebo QW until Week 51 for the weeks in between izokibep doses to maintain the blind.

The first dose of study drug (ie, izokibep or placebo) will be administered on Day 1 (Week 0).

Randomization will be stratified by any prior treatment with a systemic TNFi (Yes/No) and enthesitis (LEI > 0/LEI = 0). Anticipated enrollment of subjects previously treated with TNFi is 20% to 30%. The number of subjects without enthesitis entering into the study (LEI = 0 at baseline) will be capped at 70%.

Subjects will complete study assessments according to the study visits outlined in the Schedule of Activities (SoA; [Section 1.3](#)). The primary endpoint will be assessed at Week 16. The last dose of study drug will be administered on Week 51.

Starting at Week 24, subjects who do not meet clinical Disease Activity for PsA (cDAPSA) low disease activity (cDAPSA ≤ 14) at 2 consecutive visits (e.g. at Week 20 and Week 24) will be discontinued from study drug and can receive SOC as deemed appropriate by the Investigator.

An End of Treatment visit will be conducted at Week 52. A Safety Follow-up visit will be conducted at Week 59. A PK/anti-drug antibody (ADA) Follow-up and End of Study Visit will be conducted at Week 65.

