9.5. Sample Size Determination

Response rates for ACR50 are expected to be 20% for placebo and 45% for a dose regimen of 160 mg izokibep (QW or Q2W or both). With 100 subjects receiving placebo and 100 subjects receiving a dose regimen of 160 mg izokibep, there will be 97% power to show a difference in the primary endpoint of ACR50 response rate. If a 45% response rate is observed with a dose regimen of izokibep, the 2-sided 95% confidence interval for the true response rate will have a half-width of approximately 10 percentage points.

Up to 60% of subjects are expected to have enthesitis at baseline, based on the LEI. Response rates, proportion of subjects who have LEI = 0 at Week 16, are expected to be 25% for placebo and 60% for subjects receiving izokibep, with on treatment groups combined. With 50 subjects with enthesitis at baseline receiving placebo and 50 subjects receiving a dose regimen of izokibep, there will be 95% power to show a difference in the secondary endpoint of resolution of enthesitis. A lower rate of enthesitis at baseline will result in a lower power, but power will be at least 80% with the same assumptions on response rate, if 30 subjects with enthesitis at baseline receive placebo and 30 subjects receive a dose regimen of izokibep.

With 25 subjects receiving izokibep 80 mg Q4W, the 2-sided 95% confidence interval for the true response rate will have a half-width of up to approximately 20 percentage points.

10. Supporting Documentation and Operational Considerations

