## 6.6.2. Supplementary Analyses for the Primary Efficacy Analysis

**Tipping point analysis:** A tipping point analysis will be performed in order to evaluate the robustness of the results of the primary analysis. This analysis will use simulations to assess the impact of different response rates in subjects with missing primary endpoint data, and how different the response rates must be to change the conclusions of the study. The tipping point analysis will impute mean response rates in the two groups. Imputed response rates will be based on the response rates among subjects with observed primary endpoint data at Week 16. Sets of imputed mean response rates will include the observed response rates ( $\hat{\pi}_{ABY}$ ,  $\hat{\pi}_{PBO}$ ), as observed in each stratum, and rates that differ in increments of  $\pm 0.02$ , adjusted independently in each arm. For each of the 121 imputed mean response rates ( $\hat{\pi}_{ABY} + a$ ,  $\hat{\pi}_{PBO} + b$ ), with  $a$  and  $b$  each taking on all values from  $-0.10$  to  $+0.10$  in increments of  $0.02$ , 1000 simulations will be reported. Within each simulation, a random number mechanism will be used to assign each subject who is missing the primary endpoint at Week 16 to either response or non-response. The primary stratified analysis will be reported on each simulation, and the probability that the null hypothesis of equal response rates is rejected will be reported for each set of imputed response rates. A graphical output will summarize the rejection probability for various sets of response rates. The same tipping point analysis will be performed in comparing each izokibep group to placebo.

**Multiple Imputation:** Multiple imputation using a Markov chain Monte Carlo (MCMC) technique will be implemented to replace missing endpoint data using multiple draws from a posterior predictive distribution estimated from the placebo group only. For ACR50, assuming monotone missingness pattern, missing ACR50 at Weeks 2, 4, 12 and 16 will be imputed by first imputing the 7 components of the ACR50 criteria (SJC66, TJC68, subject's VAS assessment of pain, SGADA, IGADA, HAQ-DI, and CRP), then assigning ACR50

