status from the imputed values. Predictors in the regression model for missing values at Week 2 will be the randomization stratification factors of prior TNFi use, and LEI>0/LEI=0, as well as sex (male/female), race (white/non-white), age (continuous), and BMI (continuous). For each of the 7 components, baseline value will be included as a continuous predictor. Predictors in the regression model for missing values after Week 2 will be all of these variables, plus the value of the component being predicted at all prior scheduled assessments. Missing ACR50 values in both the placebo group and three izokibep groups will be imputed using observed data from the placebo group only. Data will be processed sequentially by repeatedly calling SAS® PROC MI to impute missing outcomes. A total of 100 imputations will be imputed to form the complete data set with a pre-specified seed (6848251) to ensure reproducibility. These multiple imputed data sets are then analyzed by using the same method for the primary analysis for complete data as specified in Section 6.6.1. The final inference on treatment difference is conducted from the multiple datasets using Rubin's combining rules. Other imputation, fully conditional specification method may be implemented if the multiple imputation model does not converge. Sample SAS code:

```
proc mi n impute=100 seed=6848251;
  var acr50;
  ods select misspattern;
run;
```

**VAS Supplemental Analyses:** A supplemental primary analysis using the VAS data on a scale from 0 to 100 mm will be performed in order to evaluate the robustness of the results when variations in the collection of the VAS data were reported by the investigator. The impact of VAS collection on paper (single vertical line through the VAS at the point that best corresponds to their feeling of pain), VAS collection via verbal response from the subject, and VAS scales that measured 100 mm will be examined by conducting the following analyses:

- Using only VAS data collected on a 0 to 100 scale (paper or verbal), excluding data collected on a 0 to 10 scale.
- Using only VAS data collected on a 0 to 100 horizontal line (paper only), excluding data collected verbally.
- Using only VAS data collected on a 0 to 100 scale (paper only, with line that measured 100 mm), excluding those collected with lines of a different length (0 to 10, 0 to <100mm, 0 to >100mm), excluding data collected verbally.

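### The tipping-point analysis reports an unpooled rejection share for each cell and names no share that counts as tipped, so its boundary is undefined and is not a test at the 0.05 level

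*Protocol*

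**What the plan says.** Protocol 9.3.2 and the tipping-point paragraph of SAP 6.6.2 describe the same procedure. Each subject with a missing Week 16 ACR50 is assigned at random to response or non-response at a set rate. The primary stratified analysis is run on the filled dataset, and this is done 1000 times for each set of rates. For each set, "the probability that the null hypothesis of equal response rates is rejected will be reported for each set of imputed response rates", with a graph. The SAP fixes the grid: shifts of −0.10 to +0.10 in steps of 0.02, independently in each arm, which gives 11 × 11 = 121 cells.

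The stated aim is to learn "how different the response rates must be to change the conclusions of the study". Neither document says what rejection probability counts as a changed conclusion.

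The test run on each filled dataset is the primary one: the Cochran-Mantel-Haenszel-weighted risk difference over its standard error, referred to the normal distribution. For the separate placebo-based multiple imputation of the same endpoint, SAP 6.6.2 does pool: "The final inference on treatment difference is conducted from the multiple datasets using" Rubin's combining rules.

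**The concern.** A tipping-point analysis should show where, on the grid of missing-data assumptions, the conclusion is lost. Two features of this one prevent that.

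First, the standard error in each of the 1000 tests treats filled values as observed. It leaves out the variation between fills, and nothing later in the procedure restores it.

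Second, the output for a cell is the share of fills that reject. That share measures how often one random fill lands past the critical value. It is not a p-value, and it crosses no natural line when the evidence crosses 0.05. With no share prespecified, the same graph can be read at 50%, 80% or 95%, and the choice can be made after the results are known.

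ACR50 for QW against placebo is the gate to every later confirmatory test, and this is the robustness check that the protocol names for it. An ambiguous boundary matters most when the result is close.

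**Working it through.** **Inputs.**
- Level: "Hypotheses tested will be adjusted to control the familywise error rate in the strong sense at" 0.05 (Protocol 9.1.1), and "All hypothesis tests will be reported with 2-sided" p-values (Protocol 9.3.1), so the critical value is 1.96.
- Rates: "Response rates for ACR50 are expected to be 20% for placebo and 45% for a dose regimen of 160 mg izokibep" (Protocol 9.5).
- Size: 100 placebo and "100 subjects receiving a dose regimen of 160 mg izokibep, there will be 97% power to show a difference" (Protocol 9.5). "Subjects meeting eligibility criteria will be randomized into 1 of 4 treatment groups in a 4:4:4:1 ratio" (Protocol 4.1), so each 160 mg comparison is 1:1.
- Missing fraction m: not in the documents. I assume 10% and 20%, with 5% to 30% as the range.
- The calculations are unstratified. The standard-error ratio depends mainly on m, so stratification should change it little.

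**The plan's own figure.** Pooled-variance SE = √(2 × 0.325 × 0.675 / 100) = 0.0662. Unpooled SE = √((0.20 × 0.80 + 0.45 × 0.55) / 100) = 0.0638. Power = Φ((0.25 − 1.96 × 0.0662) / 0.0638) = Φ(1.88) = 97.0%. The stated 97% reproduces.

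**Standard error.** Let W be the complete-data variance of the difference. With fills at rates near the observed ones, the between-fill variance is B ≈ mW. With 1000 fills Rubin's total is W + B, so pooled SE / used SE = √(1 + m).
- m = 0.10: √1.10 = 1.049
- m = 0.20: √1.20 = 1.095

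Adding uncertainty in the observed rates gives 1.054 and 1.118. Over 5% to 30% missing, the ratio runs from 1.025 to 1.140 (1.026 to 1.195 with that addition).

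**What rejection share matches pooled p = 0.05?** Over the fills, z is roughly normal with mean D/√W and variance m, where D is the mean difference over fills. Pooled p = 0.05 means D/√W = 1.96√(1 + m), so

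share = Φ(1.96 × (√(1 + m) − 1) / √m)

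- m = 0.10: Φ(1.96 × 0.0488 / 0.316) = Φ(0.30) = 62%
- m = 0.20: Φ(1.96 × 0.0954 / 0.447) = Φ(0.42) = 66%

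Over 5% to 30% missing, the matching share runs from about 59% to 69% (76% with uncertainty in the observed rates).

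**What pooled p does each cut-off imply?** For cut-off c, pooled z = (1.96 + z_c√m) / √(1 + m).

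| Cut-off share | m = 0.10 | m = 0.20 |
|---|---|---|
| 50% | p = 0.062 | p = 0.074 |
| 80% | p = 0.034 | p = 0.033 |
| 95% | p = 0.018 | p = 0.014 |

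**A cell where the readings disagree.** Observed 26/80 vs 16/80, 20 missing per arm, zero shift. D = 0.325 − 0.200 = 0.125. W = 0.003786 and B = 0.000759. Exact enumeration of the fills gives 55% rejection. Pooled z = 0.125 / √0.004545 = 1.854, so p = 0.064 (0.069 with uncertainty in the observed rates). Most fills reject, yet the pooled test does not.

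**How far the boundary moves.** Observed 36% vs 20%, 20% missing, izokibep shifted down and placebo up by s. The p range runs from simple pooling to pooling with uncertainty in the observed rates.

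| s | Rejection share | Pooled p |
|---|---|---|
| 0.04 | 78% | 0.034–0.037 |
| 0.06 | 68% | 0.045–0.050 |
| 0.08 | 57% | 0.059–0.065 |
| 0.10 | 46% | 0.077–0.083 |

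The pooled test tips at 0.08. A 50% rule tips at 0.10, one step later. An 80% rule tips at 0.04, two steps earlier.

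**At the planning rates.** In the worst corner (izokibep −0.10, placebo +0.10) with 20% missing, D = 0.8 × 0.25 + 0.2 × (0.35 − 0.30) = 0.21. The share is 99.7% and pooled p is 0.003–0.004. With 30% missing, the share is 96.8% and p is 0.009–0.012. By the pooled test, or by reading the share at any cut-off up to 95%, nothing tips.

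**The case against.** The case on the other side is substantial.

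A reader might infer that the method always places the tipping point too far out and so overstates robustness. The documents do not support this, because the direction depends on a cut-off that they do not give. At 80% or 95% the boundary is drawn too close. Nor do cells that have lost significance always look mostly significant: 31/90 vs 20/90 with 10 missing per arm gives 45% rejection at pooled p = 0.065, and 32/90 gives 66% at 0.045. A 50% reading and the pooled test agree in both. They part only when pooled p lies between 0.05 and about 0.062 (10% missing) or 0.074 (20% missing).

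A reader might also infer an inflated type I error. A single filled dataset does reject a true null more than 5% of the time, but the plan takes no decision from one fill, and the confirmatory test uses non-responder imputation.

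The text also says that the stratified analysis is reported on each simulation, so the rejection share is not strictly the only output. The multiple imputation draws all arms from placebo data, so it would differ from this analysis even with identical pooling. In a grid of stipulated rates, adding uncertainty in the observed rates is partly a matter of preference.

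All of this stands, and it limits the size and direction of the point. It does not supply the missing cut-off or a summary of the cell that can be read at 0.05.

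**Conclusion.** The point holds as a defect of definition in a supplementary analysis. Followed exactly, the plan cannot deliver its stated aim, because it never says when a cell has tipped, and the quantity it reports does not correspond to a fixed significance level. The standard error inside each test is smaller than the pooled one, which is about 5% larger at 10% missing and 10% larger at 20%. A share of about 62% or 66% would match pooled p = 0.05.

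In practice this matters only for borderline results. These sizes rest on assumed missing rates and unstratified calculations with 100 per arm. No bias in one direction and no loss of error control in the primary test can be claimed.

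**What to change.** In Protocol 9.3.2 and SAP 6.6.2, for every pair of shifts, combine the Mantel-Haenszel risk difference and its standard error across the filled datasets by Rubin's rules. Report the pooled difference, 95% confidence interval and p-value for each cell, and define the tipping boundary as the cells with pooled p ≥ 0.05. Hold shifted rates within 0 to 1. Do the same for Q2W against placebo.

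The 1000 fills already planned can serve as the imputed datasets. Drawing the observed rates from their posterior is an optional refinement; it needs a stated prior and adds little at modest missing rates. The rejection-share graph can stay as a descriptive extra.

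A lighter alternative is to prespecify the rejection share that counts as tipping. That removes the ambiguity, but no single share corresponds to 0.05, because the matching share changes with the missing fraction.

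The cost is a wording change in both documents, a little programming, and a boundary that may move by about one grid step from a 50% reading. Trial conduct and the primary analysis do not change.
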